10.1.2 Definition of serious adverse events

A serious adverse event is an AE occurring during any study phase (i.e., screening, run-in, treatment, wash-out, follow-up), at any dose of the study drugs that fulfils one or more of the following criteria:

Results in death

Is immediately life-threatening

Requires in-patient hospitalization or prolongation of existing hospitalization

Results in persistent or significant disability or incapacity

Is a congenital abnormality or birth defect in offspring of the subject

Is an important medical event that may jeopardize the patient or may require medical intervention to prevent one of the outcomes listed above:

- Medical or scientific judgment should be exercised in deciding whether expedited reporting is appropriate in this situation. Examples of medically important events are intensive treatment in an emergency room or at home for allergic bronchospasm, blood dyscrasias, or convulsions that do not result in hospitalizations; or development of drug dependency or drug abuse (21 CFR 312.32).

Important medical events, as defined above, also may be considered SAEs. Any important medical event can and will be reported as an SAE if deemed appropriate by the Principal Investigator or The University of Texas MD Anderson Cancer Center's IND Office.

All events occurring during the conduct of a protocol and meeting the definition of a SAE must be reported to the IRB in accordance with the timeframes and procedures outlines in the "The University of Texas MD Anderson Cancer Center Institutional Review Board Policy for Investigators on Reporting Serious Unanticipated Adverse Events for Drugs and Devices". Unless stated otherwise in the protocol, all SAEs, expected or unexpected, must be reported to the IND Office, regardless of attribution (within 5 working days of knowledge or the event).

All life-threatening or fatal events, that are unexpected, and related to the study drug, must have a written report submitted within 24 hours (next working day) of knowledge of the event to the Safety Project Manager in the IND Office.

Unless otherwise noted, the electronic SAE application (eSAE) will be utilized for safety reporting to the IND Office and The University of Texas MD Anderson Cancer Center IRB.

SAEs will be captured from the time of the first protocol-specific intervention, until 90 days after the last dose of study drug (durvalumab + tremelimumab), unless the participant withdraws consent. SAEs must be followed until clinical recovery is complete and laboratory tests have returned to baseline, progression of the event has stabilized, or there has been acceptable resolution of the event.

Additionally, any serious adverse events that occur after the 90 day time period that are related to the study treatment must be reported to the IND Office. This may include development of a secondary malignancy.

Reporting to FDA:

SAEs will be forwarded to the FDA by the IND Sponsor (Safety Project Manager IND Office) according to 21 CFR 312.32.

The Principal Investigator and research team will ensure SAEs are reported according to the Code of Federal Regulations, Good Clinical Practices, the protocol guidelines, the sponsor's guidelines, and Institutional Review Board policy.

10.1.3 The causality of SAEs (their relationship to all study treatment/procedures) will be assessed by the investigator(s) and communicated to AstraZeneca. Durvalumab + tremelimumab adverse events of special interest

An adverse event of special interest (AESI) is one of scientific and medical interest specific to understanding of the Investigational Product and may require close monitoring and rapid communication by the investigator to AstraZeneca/MedImmune. An AESI may be serious or non-serious. The rapid reporting of AESIs allows ongoing surveillance of these events in order to characterize and understand them in association with the use of this investigational product.

AESIs for durvalumab and tremelimumab include but are not limited to events with a potential inflammatory or immune-mediated mechanism and which may require more frequent monitoring and/or interventions such as steroids, immunosuppressants and/or hormone replacement therapy. These AESIs are being closely monitored in clinical studies with durvalumab monotherapy and combination therapy. An immune-related adverse event (irAE) is defined as an adverse event that is associated with drug exposure and is consistent with an immune-mediated mechanism of action and where there is no clear alternate etiology. Serologic, immunologic, and histologic (biopsy) data, as appropriate, should be used to support an irAE diagnosis. Appropriate efforts should be made to rule out neoplastic, infectious, metabolic, toxin, or other etiologic causes of the irAE.

If the Investigator has any questions in regards to an adverse event (AE) being an irAE, the Investigator should promptly contact [name] and/or [name].

AESIs observed with durvalumab and tremelimumab include:

- Colitis
- Pneumonitis
- ALT/AST increases / hepatitis / hepatotoxicity
- Neuropathy / neuromuscular toxicity (i.e. events of encephalitis, peripheral motor and sensory neuropathies, Guillain-Barré, and myasthenia gravis)
- Endocrinopathy (i.e. events of hypophysitis, adrenal insufficiency, and hyper- and hypothyroidism)
- Dermatitis
- Nephritis
- Pancreatitis (or labs suggestive of pancreatitis - increased serum lipase , increased serum amylase)
- Infusion related / Hypersensitivity / Anaphylactic reactions
- Other immune-mediated events that are rare could be reported (e.g. uveitis)

Further information on these risks (e.g. presenting symptoms) can be found in the current version of the durvalumab and tremelimumab Investigator Brochure. For durvalumab and tremelimumab, AESIs will comprise the following:

Pneumonitis

AEs of pneumonitis are also of interest for AstraZeneca, as pneumonitis has been observed with use of anti-PD-1 mAbs (but not with anti-PD-L1 mAbs). Initial work-up should include a high-resolution CT scan, ruling out infection, and pulse oximetry. Pulmonary consultation is highly recommended. Guidelines for the management of patients with immune-related AEs (irAEs) including pneumonitis are provided in Appendix 1.

Infusion reactions

AEs of infusion reactions (also termed infusion-related reactions) are of special interest to AstraZeneca and are defined, for the purpose of this protocol, as all AEs occurring from the start of IP infusion up to 48 hours after the infusion start time. For all infusion reactions, SAEs should be reported to AstraZeneca Patient safety as described in Section 10.3.

Hypersensitivity reactions

Hypersensitivity reactions as well as infusion-related reactions have been reported with anti-PD-L1 and anti-PD-1 therapy (Brahmer et al 2012). As with the administration of any foreign protein and/or other biologic agents, reactions following the infusion of mAbs can be caused by various mechanisms, including acute anaphylactic (IgE-mediated) and anaphylactoid reactions against the mAbs and serum sickness. Acute allergic reactions may occur, may be severe, and may result in death. Acute allergic reactions may include hypotension, dyspnea, cyanosis, respiratory failure, urticaria, pruritus, angioedema, hypotonia, arthralgia, bronchospasm, wheeze, cough, dizziness, fatigue, headache, hypertension, myalgia, vomiting, and unresponsiveness. Guidelines for the management of patients with hypersensitivity (including anaphylactic reaction) and infusion-related reactions are provided in Appendix 1.

Hepatic function abnormalities (hepatotoxicity)

Hepatic function abnormality is defined as any increase in ALT or AST to greater than $3 \times$ ULN and concurrent increase in total bilirubin to be greater than $2 \times$ ULN. Concurrent findings are those that derive from a single blood draw or from separate blood draws taken within 8 days of each other. Follow-up investigations and inquiries will be initiated promptly by the investigational site to determine whether the findings are reproducible and/or whether there is objective evidence that clearly supports causation by a disease (eg, cholelithiasis and bile duct obstruction with distended gallbladder) or an agent other than the IP. Guidelines for management of patients with hepatic function abnormality are provided in Appendix 1.

Lab abnormalities meeting the Potential Hy's Law criteria (increase in serum ALT or AST $\geq 3 \times$ ULN together with total bilirubin $\geq 2 \times$ ULN, irrespective of serum alkaline phosphatase, at any point during the study following the start of the immunotherapy agent) or Hy's Low (increase in serum ALT or AST

$\geq 3 \times \text{ULN}$ together with total bilirubin $\geq 2 \times \text{ULN}$, where no other reason can be found to explain the combination of increases, for example, elevated serum alkaline phosphatase indicating cholestasis, viral hepatitis, or another suspect drug) will be handled as per Astra-Zeneca standard operating procedures (Appendix 1).

Gastrointestinal disorders

Diarrhea/colitis is the most commonly observed treatment emergent SAE when tremelimumab is used as monotherapy. In rare cases, colon perforation may occur that requires surgery (colectomy) or can lead to a fatal outcome if not properly managed. Guidelines on management of diarrhea and colitis in patients receiving tremelimumab are provided in Appendix 1.

Endocrine disorders

Immune-mediated endocrinopathies include hypophysitis, adrenal insufficiency, and hyper- and hypothyroidism. Guidelines for the management of patients with immune-mediated endocrine events are provided in Appendix 1.

Pancreatic disorders

Immune-mediated pancreatitis includes autoimmune pancreatitis, and lipase and amylase elevation. Guidelines for the management of patients with immune-mediated pancreatic disorders are provided in Appendix 1.

Neurotoxicity

Immune-mediated nervous system events include encephalitis, peripheral motor and sensory neuropathies, Guillain-Barré, and myasthenia gravis. Guidelines for the management of patients with immune-mediated neurotoxic events are provided in Appendix 1.

Nephritis

Consult with Nephrologist. Monitor for signs and symptoms that may be related to changes in renal function (e.g. routine urinalysis, elevated serum BUN and creatinine, decreased creatinine clearance, electrolyte imbalance, decrease in urine output, proteinuria, etc.).

Patients should be thoroughly evaluated to rule out any alternative etiology (e.g., disease progression, infections etc.).

Steroids should be considered in the absence of clear alternative etiology even for low grade events (Grade 2), in order to prevent potential progression to higher grade event. Guidelines for the management of patients with immune-mediated neurotoxic events are provided in Appendix 1.

10.1.4 Immune-related adverse events

Based on the mechanism of action of durvalumab and tremelimumab leading to T-cell activation and proliferation, there is a possibility of observing irAEs during the conduct of this study. Potential irAEs may be similar to those seen with the use of ipilimumab, BMS-936558 (anti-PD-1 mAb), and BMS-936559 (anti-PD-L1 mAb) and may include immune-mediated enterocolitis, dermatitis, hepatitis

(hepatotoxicity), pneumonitis, and endocrinopathies (Hodi et al 2010, Brahmer et al 2012, Topalian et al 2012). These AEs are inflammatory in nature and can affect any organ. With anti-PD-L1 and anti-CTLA-4 combination therapy, the occurrence of overlapping or increasing cumulative toxicities that include irAEs could potentially occur at higher frequencies than with either durvalumab or tremelimumab monotherapy. Patients should be monitored for signs and symptoms of irAEs. In the absence of an alternate etiology (eg, infection or PD), an immune-related etiology should be considered for signs or symptoms of enterocolitis, dermatitis, pneumonitis, hepatitis, and endocrinopathy. In addition to the dose modification guidelines provided in Table 1, it is recommended that irAEs are managed according to the general treatment guidelines outlined for ipilimumab (Weber et al 2012). These guidelines recommend the following:

- Patients should be evaluated to identify any alternative etiology.
- In the absence of a clear alternative etiology, all events of an inflammatory nature should be considered immune related.
- Symptomatic and topical therapy should be considered for low-grade events.
- Systemic corticosteroids should be considered for a persistent low-grade event or for a severe event.
- More potent immunosuppressives should be considered for events not responding to systemic steroids (eg, infliximab or mycophenolate).

10.2 If the Investigator has any questions in regards to an AE being an irAE, the Investigator should immediately contact [name] and/or [name]. Assessment of safety parameters

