Appendix 1. Dosing Modification and Toxicity Management Guidelines for Immune-mediated, Infusion Related, and Non Immune-mediated Reactions (MEDI4736 Monotherapy or Combination therapy with Tremelimumab or Tremelimumab Monotherapy) 19 August 2016 Version

Dose Modifications	Toxicity Management

Drug administration modifications of study drug/study regimen will be made to manage potential immune-related AEs based on severity of treatment-emergent toxicities graded per NCI CTCAE v4.03.
 
In addition to the criteria for permanent discontinuation of study drug/study regimen based on CTC grade/severity (table below), permanently discontinue study drug/study regimen for the following conditions:
 
 • Inability to reduce corticosteroid to a dose of ≤ 10 mg of prednisone per day (or equivalent) within 12 weeks after last dose of study drug/study regimen • Recurrence of a previously experienced Grade 3 treatment-related AE following resumption of dosing 
Grade 1 No dose modification
 
Grade 2 Hold study drug/study regimen dose until Grade 2 resolution to Grade ≤ 1.
 
If toxicity worsens, then treat as Grade 3 or Grade 4.
 
Study drug/study regimen can be resumed once event stabilizes to Grade ≤ 1 after completion of steroid taper.
 
Patients with endocrinopathies who may require prolonged or continued steroid replacement can be retreated with study drug/study regimen on the following conditions:
 
 1. The event stabilizes and is controlled. 2. The patient is clinically stable as per Investigator or treating physician's clinical judgement. 	
It is recommended that management of irAEs follows the guidelines presented in this table:
 
 – Patients should be thoroughly evaluated to rule out any alternative etiology (eg, disease progression, concomitant medications, and infections). – In the absence of a clear alternative etiology, all events should be considered potentially immune related. – Symptomatic and topical therapy should be considered for low-grade (Grade 1 or 2, unless otherwise specified) events. – For persistent (>3 to 5 days) low-grade (Grade 2) or severe (Grade ≥ 3) events, promptly start prednisone 1 to 2 mg/kg/day PO or IV equivalent. – If symptoms recur or worsen during corticosteroid tapering (28 days of taper), increase the corticosteroid dose (prednisone dose [eg, up to 2 to 4 mg/kg/day PO or IV equivalent]) until stabilization or improvement of symptoms, then resume corticosteroid tapering at a slower rate (>28 days of taper). – More potent immunosuppressives such as TNF inhibitors (eg, infliximab) (also refer to the individual sections of the irAE for specific type of immunosuppressive) should be considered for events not responding to systemic steroids. – Discontinuation of study drug/study regimen is not mandated for Grade 3/Grade 4 inflammatory reactions attributed to local tumor response (eg, inflammatory reaction at sites of metastatic disease and lymph nodes). Continuation of study drug/study regimen in this situation should be based upon a benefit/risk analysis for that patient.

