	Grade 2 (symptomatic; medical intervention indicated; limiting instrumental ADL)	Hold study drug/study regimen dose until Grade 2 resolution to Grade \leq 1. 
 • If toxicity worsens, then treat as Grade 3 or Grade 4. • If toxicity improves to Grade \leq1, then the decision to reinstate study drug/study regimen will be based upon treating physician’s clinical judgment and after completion of steroid taper. 	
For Grade 2 (mild to moderate new symptoms):
 
 – Monitor symptoms daily and consider hospitalization. – Promptly start systemic steroids (eg, prednisone 1 to 2 mg/kg/day PO or IV equivalent). – Reimage as clinically indicated. – If no improvement within 3 to 5 days, additional workup should be considered and prompt treatment with IV methylprednisolone 2 to 4 mg/kg/day started – If still no improvement within 3 to 5 days despite IV methylprednisone at 2 to 4 mg/kg/day, promptly start immunosuppressive therapy such as TNF inhibitors (eg, infliximab at 5 mg/kg every 2 weeks). Caution: It is

Specific Immune-mediated Reactions

Adverse Events	Severity Grade of the Event (NCI CTCAE version 4.03)	Dose Modifications	Toxicity Management
			
important to rule out sepsis and refer to infliximab label for general guidance before using infliximab.
 
 - Once the patient is improving, gradually taper steroids over ≥ 28 days and consider prophylactic antibiotics, antifungals, or anti-PCP treatment (refer to current NCCN guidelines for treatment of cancer-related infections (Category 2B recommendation)^a - Consider pulmonary and infectious disease consult. - Consider, as necessary, discussing with [name] and/or [name].

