	
Grade 3 or 4 (Grade 3: stool frequency of ≥ 7 over baseline per day; Grade 4: life threatening consequences)
	
Permanently discontinue study drug/study regimen.
	
For Grade 3 or 4:
 
 - Promptly initiate empiric IV methylprednisolone 2 to 4 mg/kg/day or equivalent. - Monitor stool frequency and volume and maintain hydration. - Urgent GI consult and imaging and/or colonoscopy as appropriate. - If still no improvement within 3 to 5 days of IV methylprednisolone 2 to 4 mg/kg/day or equivalent, promptly start further immunosuppressives (eg infliximab at 5 mg/kg once every 2 weeks). Caution: Ensure GI consult to rule out bowel perforation and refer to infliximab label for general guidance before using infliximab. - Once the patient is improving, gradually taper steroids over ≥ 28 days and consider prophylactic antibiotics, antifungals, and anti-PCP treatment (refer to current NCCN guidelines for

Specific Immune-mediated Reactions

Adverse Events	Severity Grade of the Event (NCI CTCAE version 4.03)	Dose Modifications	Toxicity Management
			treatment of cancer-related infections [Category 2B recommendation]). ^a
Hepatitis (elevated LFTs) Infliximab should not be used for management of immune-related hepatitis.	Any Grade	General Guidance	For Any Grade: 
 – Monitor and evaluate liver function test: AST, ALT, ALP, and TB. – Evaluate for alternative etiologies (eg, viral hepatitis, disease progression, concomitant medications).
	Grade 1 AST or ALT > to 3 × ULN and/or TB > to 1.5 × ULN)	No dose modifications. 
 • If it worsens, then treat as Grade 2 event. 	For Grade 1: 
 – Continue LFT monitoring per protocol.

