	Grade 2 (AST or ALT > 3 to 5 × ULN and/or TB >1.5 to 3.0 × ULN)	Hold study drug/study regimen dose until Grade 2 resolution to Grade ≤1. 
 • If toxicity worsens, then treat as Grade 3 or Grade 4. • If toxicity improves to Grade ≤1 or baseline, resume study drug/study regimen after completion of steroid taper. 	For Grade 2: 
 – Regular and frequent checking of LFTs (eg, every 1 to 2 days) until elevations of these are improving or resolved. – If no resolution to Grade ≤1 in 1 to 2 days, discuss with [name] and/or [name]. – If event is persistent (>3 to 5 days) or worsens, promptly start prednisone 1 to 2 mg/kg/day PO or IV equivalent. – If still no improvement within 3 to 5 days despite 1 to 2 mg/kg/day of prednisone PO or IV equivalent, consider additional workup and start prompt treatment with IV methylprednisolone 2 to 4 mg/kg/day. – If still no improvement within 3 to 5 days despite 2 to 4 mg/kg/day of IV methylprednisolone, promptly start immunosuppressives (mycophenolate mofetil)^a Discuss with [name] and/or [name] if mycophenolate mofetil is not available. Infliximab should NOT be used.

Specific Immune-mediated Reactions

Adverse Events	Severity Grade of the Event (NCI CTCAE version 4.03)	Dose Modifications	Toxicity Management
			
 Once the patient is improving, gradually taper steroids over ≥ 28 days and consider prophylactic antibiotics, antifungals, and anti-PCP treatment (refer to current NCCN guidelines for treatment of cancer-related infections [Category 2B recommendation]).^a

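### Section 10.1.4 offers infliximab for steroid-refractory immune-related events with no exception for hepatitis, Appendix 1 rules it out for hepatitis, and nothing says which text governs

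*Combined protocol and SAP*

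**What the plan says.** Two parts of the protocol give guidance on treating irAEs.

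**Section 10.1.4.** After describing the expected irAEs, with hepatitis among them, it says that "an immune-related etiology should be considered for signs or symptoms of enterocolitis, dermatitis, pneumonitis, hepatitis, and endocrinopathy" when no other cause is found. It then brings in outside guidance, on top of the dose changes that it locates in Table 1. Its words are: "it is recommended that irAEs are managed according to the general treatment guidelines outlined for ipilimumab". It summarizes that guidance in five bullets, the last of which reads: "More potent immunosuppressives should be considered for events not responding to systemic steroids (eg, infliximab or mycophenolate". No bullet singles out an organ.

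**Appendix 1.** Its general row says: "It is recommended that management of irAEs follows the guidelines presented in this table". That row also gives infliximab as an example for events that fail systemic steroids, but in the same sentence it sends the reader to the individual event sections for the type of immunosuppressive. The heading of the hepatitis row then says: "Infliximab should not be used for management of immune-related hepatitis". The Grade 2 and Grade 3 or 4 hepatitis rows each repeat "Infliximab should NOT be used" and name mycophenolate mofetil.

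**Pointers elsewhere.** Section 6.3.1 says that toxicity management for immune-mediated reactions is set out in Appendix 1. Section 10.1.3 refers hepatic function abnormality, among other events, to Appendix 1.

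**The concern.** Section 10.1.4 looks like a self-contained instruction for treating irAEs. It names hepatitis, recommends a guideline and lists two drugs for steroid failure. One of those two is the drug that Appendix 1 excludes for hepatitis. Someone treating steroid-refractory immune-related hepatitis at the site from Section 10.1.4 alone would find infliximab listed as an option and nothing to suggest otherwise.

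What is at stake is patient safety and consistent treatment. Under the protocol as printed, one clinician could follow Section 10.1.4 and another Appendix 1, and each could claim to have complied.

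**Working it through.** No figure in the plan is in question, so there is nothing to recompute. The check is a comparison of wording, followed by a search for text that would settle the difference.

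| Feature | Section 10.1.4 | Appendix 1 |
|---|---|---|
| Events covered | irAEs in general; hepatitis named | irAEs in general; a separate hepatitis row |
| Guidance to follow | Outside ipilimumab guideline, in addition to dose modification rules | Its own table |
| Agents named for steroid failure in general | Infliximab or mycophenolate, as examples | TNF inhibitors such as infliximab, as an example |
| Hepatitis | No exception | Infliximab excluded in three places; mycophenolate mofetil named |
| Referral to organ-specific text | None | Yes, in the general row |

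1. **Does Section 10.1.4 cover hepatitis?** Yes. It appears both in the list of potential irAEs and in the list of presentations for which an immune cause should be considered.
2. **Is the exclusion in Appendix 1 explicit?** Yes. It stands in the row heading, at Grade 2 and at Grade 3 or 4.
3. **Does Section 10.1.4 lead the reader to the exclusion?** No. Its only internal cross-reference is to Table 1 for dose modification. Table 1, printed in Sections 3.3 and 11.5, holds the ETOX stopping criteria and nothing on dose modification or hepatitis. The ipilimumab guideline it cites has no entry in Section 12.
4. **Does other text lead there?** In part. Section 6.3.1 sends immune-mediated reactions to Appendix 1. The hepatic paragraph of Section 10.1.3 does so for hepatic function abnormality, which it defines as ALT or AST above 3 × ULN with concurrent bilirubin above 2 × ULN. The hepatitis row of Appendix 1 is wider, because it grades a rise in transaminases or bilirubin alone.
5. **Does any text rank the two sources?** None was found. Neither Section 6.3.1, Section 10.1.3, Section 10.1.4 nor Appendix 1 says which prevails if they differ.

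**The case against.** The strongest reply is that this is a general rule with a specific exception. The Section 10.1.4 bullet is permissive, gives examples only and speaks for all irAEs together. Of its two examples, mycophenolate is the agent Appendix 1 names for hepatitis, and infliximab is the one it names for pneumonitis and enterocolitis. Nothing in the protocol instructs anyone to give infliximab for hepatitis. Section 10.1.4 presents the ipilimumab guideline as an addition, and its Table 1 pointer may simply be a stale reference to the Appendix 1 table. The hepatitis rows also call for discussion with the study leads (Grade 2) and a hepatology consult (Grade 3 or 4).

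Most of this stands and limits the point. It does not remove it, because the reader has to infer the exception: Section 10.1.4 neither states it nor leads to it. Whether the cited ipilimumab guideline has its own hepatitis exception cannot be checked from the documents, so the comparison is confined to the printed bullets.

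A reader might infer two further problems that the documents do not support.

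- **Conflicting steroid timing.** Section 10.1.4 has systemic steroids considered for persistent low-grade events, while Appendix 1 starts them promptly at Grade 2 for pneumonitis and enterocolitis. But the general row of Appendix 1 also requires persistence (more than 3 to 5 days) at Grade 2, as do its Grade 2 hepatitis and nephritis rows. The difference in persistence lies within Appendix 1. Between the two texts only the strength of the verb differs.
- **An effect on the ETOX endpoint.** A steroid-treatable grade 3 or higher event counts only if it fails to improve to grade 1 or better within 2 weeks, and Appendix 1 brings in second-line treatment for Grade 3 or 4 hepatitis after 3 to 5 days without improvement. One patient can matter: with a beta(0.2 + x, 0.8 + n − x) posterior, the probability that the ETOX rate exceeds 0.20 is 0.721 at 2 of 6 and 0.927 at 3 of 6, on either side of the 0.90 limit. That would be true of any reclassified patient. The documents give no evidence that the two agents differ in 2-week recovery and do not define when the 2 weeks start. Since Section 10.1.4 also lists mycophenolate, the agent given need not differ at all.

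**Conclusion.** The point holds as an unreconciled inconsistency in treatment text: an unqualified example in Section 10.1.4, an explicit exclusion in Appendix 1, a wrong pointer, a missing reference and no statement of which text governs. It would be too strong to say that the protocol gives two opposing orders for hepatitis.

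Its reach is narrow. It matters only for a patient with steroid-refractory immune-related hepatitis, in a trial of 15 patients at one center. The documents give no rate for that event, so no expected number can be stated. It has no bearing on the sample size, the stopping boundaries or their operating characteristics.

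The conclusion rests on the printed wording alone. It takes no view on which clinical instruction is right. The change is still worth making, because the text concerns treatment of a serious event and the correction costs almost nothing.

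**What to change.** In the next amendment:

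1. Reconcile the second-line immunosuppressant bullet in Section 10.1.4 with the organ-specific rows of Appendix 1. The sponsor's clinical team decides the content.
2. State in Section 10.1.4 which text governs irAE treatment where the two differ.
3. Correct the Table 1 pointer so that it leads to the dose modification guidance intended. The context suggests the Appendix 1 table, which the sponsor should confirm.
4. Add the cited ipilimumab guideline to Section 12, or remove the citation if it is no longer relied on.

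The cost is one paragraph of protocol text and one reference entry. No procedure, patient or analysis is added.
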